8.3.3 Safety Endpoints

Safety endpoints are:

- Nature, incidence and severity of local and systemic AEs
- Incidence of acute inflammatory reactions (AIRs), defined as increase of pain by 30 mm on a 100 mm VAS associated with a self-reported synovial fluid effusion (i.e., joint swelling) within 3 days following i.a. injection
- Changes in laboratory safety parameters, vital signs, 12-lead ECG parameters, weight, and physical examinations
- Incidence of surgical interventions in the target knee (including any surgical revision, cartilage removal, or any other type of surgical intervention)
- Occurrence of binding and neutralizing antibodies to sprifermin/FGF-18

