Pairwise comparisons (sprifermin versus placebo, and between sprifermin dose and regimen groups) will be performed within the context of this modeling framework. For each pairwise comparison, the difference between treatments and the corresponding 95% confidence interval (CI) and p-value will be presented.

The primary efficacy analysis will be performed on the mITT Analysis Set.

In order to assess the robustness of the primary results, sensitivity analyses will be performed with modification of subject population (PP Analysis Set), statistical methods (influence of the distribution, influence of the time effect, and so on), and influence of covariates.

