8.5.4 Safety Analyses

Safety data will be summarized descriptively overall and by treatment group, using the Safety Analysis Set.

AEs will be coded using the latest available version of the Medical Dictionary for Regulatory Activities (MedDRA).

All local and systemic AEs will be reported overall, by severity, and by relationship to trial drug, and summaries will be prepared of events leading to discontinuation and events leading to death.

The incidence of protocol-defined AIRs and the incidence of surgical procedures occurring to the target knee during the trial will be tabulated separately.

Laboratory safety parameters and vital signs will be descriptively summarized as appropriate.

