8.4 Interim analysis

No interim analysis prior to Year-2 analysis is planned.

9 Changes to the Planned Analyses in the Clinical Trial Protocol

The following clarifications and changes (including deletion and additional analyses) compared to the protocol have been made prior to database lock and breaking the blind of the study:

Deletion:

Interleukin-6 (IL-6) is not measured (see Note to File "Selection of Biomarkers for Clinical Study EMR700692-006") and therefore was removed from the list of laboratory parameters (Section 7.4.3 of the protocol).

Clarifications:

- 1. The protocol is not specific on what deviations are considered major and resulting in subjects who are excluded from the PP Analysis (Section 8.4 of the protocol). Section 10 provides more details for definition of major protocol deviations and the process to identify them.
- 2. The protocol is not specific on how data will be included in the extended follow-up period analysis (Section 8.5.1 of the protocol). Section 8.2 provides more details on what data will be included in this analysis. It also specifies that all data from the 5 years period will be included in this integrated analysis.
- 3. Clarification on time points, scored regions, scoring system and analyses for Whole Organ Magnetic Resonance Imaging Score (WORMS) and (Boston-Leeds Osteoarthritis Knee Score) BLOKS are provided in Section 16.5 (Section 8.5.5 of the protocol).

Additions:

- 1. Analysis sets. The following additional analysis set is specified in Section 10. For the long term follow-up phase (following day 819), a separate analysis set is defined consisting of subjects from the ITT population who have at least one post-treatment quantitative MRI assessment or at least one WOMAC measurement in the follow-up period, i.e., the Second ITT (ITT2). The ITT2 Analysis Set will include all subjects from the ITT Analysis Set who have at least one MRI assessment available or one X-ray assessment available or one WOMAC measurement on or after day 820.
- 2. Year-3 Analysis: A Year-3 Analysis is planned and described in Section 8.
- 3. Sensitivity analysis using LOCF. The LOCF method as imputation for missing data on post baseline observations will be used as sensitivity evaluation with potential to be utilized in future studies. This is described in Section 11.

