LOCF2 (Up to Month 60)	Last post-baseline measurement in Follow-up period (2, 1849)	50

Adjustment for Multiplicity

The main objective of this Phase II trial is to select a dose regimen for further development in Phase III; therefore, no adjustment for multiplicity (except for dunnett adjustment for multiple comparisons used in the ANOVA models) resulting from multiple endpoints will be made. Caution should be used in interpreting significant p-values (p < 0.05). Interpretation of the results will involve global consideration of all efficacy results obtained in combination with an appropriate judgment of clinical relevance and consistency across endpoints.

Missing Data

As a general rule, all data collected and available will be used in the analysis. In general no imputation of missing data will be applied independently of the statistical method used to analyze the data, see however below remarks for LOCF in summaries over time.

The number of subjects contributing data will decrease over time. In summary assessments by time-point within DBPC, the LOCF method on post baseline observations will be used as sensitivity evaluation, and will be defined as LOCF1 for the 2-year analysis, and LOCF2 for the

analysis of the extended follow-up. These will only be included in summary tables (not in proc mixed models) and are considered exploratory and will be utilized for phase III statistical consideration. In the remainder of the SAP, if not otherwise stated, LOCF refers to both LOCF1 and LOCF2. Details for derivation of LOCF1 and LOCF2 for corresponding endpoints are provided in Table 3, 3a, and 3b.

Exceptions are handling of missing data from questionnaires where the guide for analysis prescribes otherwise, e.g. calculation depending on whether only single items are missing or a complete questionnaire is missing. If only single items are missing, the rules defined by the authors of the questionnaires (if any) will be followed.

The number and percentage of subjects with missing data for the primary and the secondary endpoints medial and lateral cartilage thickness, will be summarized by treatment group and timepoint for the mITT Analysis Set.

Listing of data

In general, all data will be listed by treatment group, subject and time point. Age, sex and race will be displayed in all listings.

ANOVA models

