ANOVA models are used for several endpoints. For each endpoint all available time-points except LOCF (specified in table 3) should be included and summarized. The general model specification for model that include 4 post-baseline measurements (i.e. qMRI) in SAS will be:

```
proc mixed data=p3 method=reml;
  class grpn vs usubjid CNTRGR1N ;
 model &var. = grpn vs grpn*vs base CNTRGR1N / solution;
  repeated vs / subject=usubjid type=&type. r;
  lsmeans grpn / adjust=dunnett diff=control('1') cl;
  lsmeans grpn*vs / adjust=dunnett diff=control('1' 'Week 26') cl;
  lsmeans grpn*vs / adjust=dunnett diff=control('1' 'Week 52') cl;
  lsmeans grpn*vs / adjust=dunnett diff=control('1' 'Week 78') cl;
 lsmeans grpn*vs / adjust=dunnett diff=control('1' 'Week 104') cl;
  lsmeans grpn*vs / slice=vs;
  contrast 'Linear trend (overall)' grpn -2 -1 0 1 2;
  contrast 'Linear trend at Week 26' grpn -2 -1 0 1 2 grpn*vs -2 0 0 0 -1 0 0
0 0 0 0 0 1 0 0 0 2 0 0 0;
  contrast 'Linear trend at Week 52' grpn -2 -1 0 1 2 grpn*vs 0 -2 0 0 0 -1 0
0 0 0 0 0 0 1 0 0 0 2 0 0;
  contrast 'Linear trend at Week 78' grpn -2 -1 0 1 2 grpn*vs 0 0 -2 0 0 0 -1
0 0 0 0 0 0 0 1 0 0 0 2 0;
  contrast 'Linear trend at Week 104' grpn -2 -1 0 1 2 grpn*vs 0 0 0 -2 0 0 0
-1 0 0 0 0 0 0 0 1 0 0 0 2;
```

run;

12 Disposition of Subjects and Discontinuations

This section presents specifications for reporting subject disposition and treatment/trial discontinuations. Additionally, procedures for reporting protocol deviations are provided.

Subject disposition will be presented for all subjects and by treatment group in terms of:

- Total number of subjects screened (i.e. subjects who signed informed consent)
- Number and percentages of subjects discontinuing the trial prior to randomization divided by main reason for discontinuation (did not meet all eligibility criteria, withdrew consent, other), by country and site, and overall.
- Number and percentages of randomized subjects.
- Number and percentages of exposed subjects
- Number and percentages of randomized subjects who completed the DBPC treatment phase. For the 2-year analysis a completer is a subject with no date of study discontinuation before day 819.
- Number and percentages of randomized subjects who discontinued the trial after randomization, during DPBC i.e. before day 819, and during extended follow up phase (grouped by treatment) and main reason (AE, death, lost to follow-up, etc).

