The treatment effect on the primary endpoint will be assessed through dose-ranging using a repeated measurement analysis of variance (ANOVA) (using PROC MIXED in SAS) on absolute change from baseline, including the treatment group, the time point, and the (pooled) country as fixed factors and the baseline value as covariate and treatment by time point as interaction, see "ANOVA models" in section 11. Repeated measures over time will be accounted for using an 'unstructured' covariance pattern, and if the model fails to converge 'compound symmetry' will be used.

If the null hypothesis is rejected, the alternative hypothesis will be accepted and it will be concluded that there is a dose relationship versus placebo over time.

The analysis of the primary efficacy endpoint will also consist of testing the overall treatment effect at 2 years and will therefore only be conducted for the DBPC treatment phase.

The significance level will be set at 5% two-sided.

For the overall treatment effect testing, the null and alternative hypotheses will be:

```
H0: Mean (Placebo) = Mean (180 mcg) = Mean (360 mcg) = Mean (600 mcg) = Mean (1200 mcg) H1: Mean (i) \neq Mean (j) for some i \neq j and i, j = Placebo or 180 mcg or 360 mcg or 600 mcg or 1200 mcg.
```

where the doses shown are the total doses of sprifermin to be administered over the DBPC treatment phase.

If the null hypothesis is rejected, the alternative hypothesis will be accepted and it will be concluded that there is at least one group that differs from the other groups.

Pairwise comparisons of absolute change from baseline in cartilage thickness (sprifermin treatment groups versus placebo) will be performed within the context of this modeling framework. For each pairwise comparison, the difference between treatments and the corresponding 95% CI and p-value will be presented. P-values (corresponding to Type 3 tests of fixed effects) will be reported for all covariates in the original 'Overall' model for all time points combined (i.e. baseline value, treatment, timepoint, treatment-by-timepoint interaction, country) and for all timepoints. Estimated coefficients, p-values and 95% CIs will be presented overall and at each timepoint for

(i) the dose relationship (linear trend); and, (ii) each pairwise comparison between dose level and placebo.

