Baseline protein markers and/or genetic markers associated with response to treatment or disease progression (response assessed by MRI and/or questionnaire)

This analysis will be done by Merck Serono and is described in a separate analysis plan. Exception is subgroup analyses by biomarker subgroups as specified in Section 16.4.

Relationship between dosing (dose and regimen), cartilage structure, and clinical scores as a function of time

This analysis will be done by Merck Serono Exploratory Medicine and is described in a separate analysis plan.

Subgroup analysis

The endpoints mentioned below will be presented for the subgroups defined in Section 10 and will be conducted only for the DBPC treatment phase for the ITT analysis set.

Endpoints:

- Cartilage thickness in the total femorotibial joint
- Cartilage thickness in the medial and lateral compartments
- WOMAC total score
- WOMAC pain and function sub scores
- 20 meter walk test
- Lateral and medial JSW (mJSW) in target knee

Data will be presented (descriptive only) as described for the primary efficacy endpoint.

Additional analyses for primary and secondary endpoints

In addition to analysing continuous variables, it is important to identify subjects who achieve meaningful clinical response (for structure and symptoms). Therefore the following variables will be derived and analysed:

Subjects who achieve meaningful clinical response for structure are considered responders if they have increase from baseline of at least 0.01 mm in MRI total femorotibial cartilage thickness. Similarly, subjects who achieve meaningful clinical response for symptoms are considered responders if they have a decrease from baseline of at least 10 points in Total WOMAC. In addition, a combination of the above 2 mentioned responder variables will be explored as potential composite responder variable (a decrease from baseline of 10 points for Total WOMAC and an increase from baseline of 0.01 mm for MRI Total femorotibial cartilage thickness).

Number and percent of subjects with total femorotibial joint thickness increase of at least 0.01mm from baseline will be summarized for all timepoints (including LOCF).

Number and percent of subjects with 10-point improvement (on a scale of 0-100) from baseline will be summarized for WOMAC Total and WOMAC sub scores at all timepoints (including LOCF).

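### The SAP drops, with no entry in its section 9, the protocol's comparisons between sprifermin regimens and its incidence table for target-knee surgery

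*SAP*

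**What the plan says.** **Comparisons between regimens.** Protocol 8.5.2, like the synopsis, states: "Pairwise comparisons (sprifermin versus placebo, and between sprifermin dose and regimen groups) will be performed". Each comparison is to be reported with a difference, a 95% CI and a p-value. SAP 16.1 states: "Pairwise comparisons of absolute change from baseline in cartilage thickness (sprifermin treatment groups versus placebo) will be performed". The results that section then lists are the linear trend and each dose level against placebo. The model code in SAP section 11 agrees. Every LSMEANS difference is taken against a placebo level, as in "lsmeans grpn*vs / adjust=dunnett diff=control('1' 'Week 104') cl", and every CONTRAST statement is a linear trend. The logistic regression estimates in SAP 16.5 are also all against placebo, and the key outputs in SAP 19.5 name no result between active arms.

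**Target-knee surgery.** Protocol 8.3.3 lists as a safety endpoint "Incidence of surgical interventions in the target knee", and protocol 8.5.4 adds: "The incidence of protocol-defined AIRs and the incidence of surgical procedures occurring to the target knee during the trial will be tabulated separately". The safety endpoints in SAP section 6 leave this item out. There is no surgery entry in SAP section 17, in the safety rows of Appendix 19.1 or in the key safety tables in 19.5.3. SAP section 14 sends procedures to listings only, while Appendix 19.1 marks procedures for descriptive summary.

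**Record of changes.** SAP section 9 opens: "The following clarifications and changes (including deletion and additional analyses) compared to the protocol have been made prior to database lock". The only deletion it names is interleukin-6.

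**The concern.** SAP section 11 gives the trial's purpose: "The main objective of this Phase II trial is to select a dose regimen for further development in Phase III". Choosing among four active regimens means comparing them with each other, and the SAP reports no difference or interval that does so. The linear trend, the overall test and the comparisons with placebo can all be significant when the four regimens are equally effective. SAP 16.1 would nevertheless read a significant trend as a dose relationship.

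The missing record matters too. Under SAP section 5, any analysis not in the SAP must be identified in the trial report as additional. A between-regimen comparison run later would then carry that label although the protocol planned it.

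The surgery item is a smaller loss. Events remain in listings by treatment group, but the by-arm incidence table of a protocol safety endpoint is gone.

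**Working it through.** **1. Count of comparisons.** Five arms give 5 × 4 / 2 = 10 pairs. The protocol covers all 10: 4 against placebo and 6 between active arms. The SAP keeps 4 and drops 6.

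**2. Inputs.** From protocol 8.1 and SAP section 7: planned 2-year mean changes of -0.03 (placebo), -0.01 (180 mcg), +0.01 (360 mcg), +0.01 (600 mcg) and +0.03 mm (1200 mcg); common SD 0.10 mm; two-sided 5%; 76 evaluable per arm. Residual df = 5 × 76 - 5 = 375. Powers use the noncentral t or F distribution.

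**3. The plan's own figures.** The trend contrast with weights (-2, -1, 0, 1, 2) equals 0.06 + 0.01 + 0 + 0.01 + 0.06 = 0.14. With 55 per arm its SE is 0.10 × √(10/55) = 0.0426, and power is 0.905 (stated 90%). The overall F test with 76 per arm has power 0.904 (stated 90%). Both reproduce.

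**4. What the trend contrast measures.** Its weights equal 2 × (mean of active arms - placebo) + 2 × (100 mcg arms - 30 mcg arms) + 1 × (twice-yearly arms - once-yearly arms). On the planning means:

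- active against placebo: 2 × 0.04 = 0.08
- dose: 2 × 0.02 = 0.04
- interval: 1 × 0.02 = 0.02

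These sum to 0.14. More than half of the contrast (0.08 of 0.14) is therefore the common effect of being on active treatment.

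**5. An illustration with no difference between regimens.** Take all four active arms at +0.01 mm and placebo at -0.03 mm. This is an assumed case.

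- Trend contrast = 0.08; SE = 0.10 × √(10/76) = 0.0363; probability of rejection 0.595.
- Overall test: the grand mean is 0.002, so the noncentrality is 76 × (0.032² + 4 × 0.008²) / 0.10² = 9.73; probability of rejection 0.696.

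**6. What the six dropped comparisons would give.** SE = 0.10 × √(2/76) = 0.0162; 95% CI half-width = 1.966 × 0.0162 = 0.032 mm.

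| Pair (total dose, mcg) | Planned difference (mm) | Power |
|---|---|---|
| 1200 - 600 | 0.02 | 0.23 |
| 1200 - 360 | 0.02 | 0.23 |
| 600 - 180 | 0.02 | 0.23 |
| 360 - 180 | 0.02 | 0.23 |
| 1200 - 180 | 0.04 | 0.69 |
| 600 - 360 | 0 | n/a |

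A contrast that pools the two 100 mcg arms against the two 30 mcg arms, or the two twice-yearly against the two once-yearly arms, has SE 0.10/√76 = 0.0115, half-width 0.0226 mm and power 0.41 at 0.02 mm.

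**7. Range for the sample size.** The mITT set needs only one post-baseline MRI and the model uses all visits, so the effective number may lie between 76 and the 109 randomized per arm. At 109, the pairwise half-width is 0.0266 mm, with power 0.31 at 0.02 mm and 0.84 at 0.04 mm. The pooled-contrast power is 0.55.

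**The case against.** The strongest reply is that little is lost.

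- **Point estimates remain.** The code requests LS means with confidence limits for every arm and visit, and an active-versus-active point difference follows by subtracting two comparisons with placebo. This is true, but the subtraction gives no CI or p-value, because both comparisons share the placebo mean. The fixed-effect solution might print some active-arm differences, but the SAP does not commit to reporting them.
- **Dose selection is done elsewhere.** Protocol 8.5.5 says the pharmacometric modelling is meant to support the choice of regimen, and SAP section 11 rests interpretation on all efficacy results together. On the relationship between dosing, structure and clinical scores, SAP 16.5 says: "This analysis will be done by Merck Serono Exploratory Medicine and is described in a separate analysis plan". That work may well inform the choice. It is a different analysis from the comparison that protocol 8.5.2 promises alongside it, and its plan is not in the file.
- **The comparisons are weak.** The half-width exceeds five of the six planned differences. This stands, and it limits how the results may be read. It is also a reason to show the intervals, since they tell the reader how poorly the trial separates the regimens.
- **Surgery is partly covered.** Target-knee arthroscopy is a prohibited procedure, and SAP 12.1 tabulates major deviations by arm and type. That table does not clearly cover other surgery and may group procedures with medications. The table shells are a separate document not available here and might contain a surgery table. Even so, SAP sections 6, 9 and 14 would still disagree with the protocol.

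**Conclusion.** The concern holds. Two analyses planned in the protocol are missing from the SAP, and section 9 records neither. The primary tests themselves are unaffected.

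The loss of the six between-regimen comparisons is the weightier part. As written, the SAP reports no direct difference or interval between active regimens, while a significant trend or overall test is likely (about 59% and 70% in the illustration) even if the regimens do not differ. The size rests on the planning SD of 0.10 mm and on 76 per arm. With up to 109 per arm the intervals narrow only to ±0.027 mm, so the comparisons remain estimates. The surgery table is a minor loss of descriptive safety reporting. That part is also less certain, because the table shells could not be seen.

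**What to change.** 1. In SAP 16.1 and the section 11 code, add the six active-versus-active differences at Week 104 with 95% CIs, labelled as estimation. The p-values that protocol 8.5.2 asks for come with the same output. If they are left out, say so in section 9. The alternative is to record the deletion of these comparisons in section 9 with a reason.
2. Optionally, add the pooled dose and interval contrasts over the four active arms, marked as additions to the protocol.
3. Restore target-knee surgery to the safety endpoints in SAP section 6, with a descriptive by-arm incidence table on the Safety Analysis Set, or record and justify its removal in section 9.
4. Reconcile section 14 (procedures listed only) with Appendix 19.1 (procedures summarized descriptively), and check that the table shells agree.

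The cost is six differences from a model already specified and one table, with no new data and no change in sample size. The downside is a set of unadjusted, imprecise intervals that could be over-read, which is why they should be labelled as estimation.

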16.2 Secondary Efficacy Endpoint Analyses

Secondary endpoints related to structure:

Cartilage thickness

Cartilage thickness in the medial and lateral compartments will be summarised per timepoint (including LOCF) along with absolute and relative change from baseline. These will be calculated in two ways corresponding to the calculation of cartilage Average and Total thickness:

- 1. Medial
 - a. MFTC.VC/(cMF.tAB+MT.tAB), primary
 - b. MFTC ThCtAB aMe
- 2. Lateral:
 - a. LFTC.VC/(cLF.tAB+LT.tAB), primary
 - b. LFTC ThCtAB aMe

All these variables will be included in the ADAM. Only (1a) and (2a) will be used in summaries and analyses, the others (1b) and (2b) will only be derived in ADaM.

The absolute change from baseline in the medial and lateral compartments over 2 years will be analysed using a similar ANOVA model as the model used for the primary endpoint. Similarly to the analysis of the primary end-point, sensitivity analyses on ranked data will also be performed.

Cartilage Volume

Cartilage volume in the medial and lateral compartments as well as in the total femorotibial joint will be summarised per timepoint (including LOCF) along with absolute and relative change from baseline. These will be calculated as MFTC.VC, LFTC.VC, and MFTC.VC + LFTC.VC respectively.

The absolute change from baseline over 2 years will be analysed using a similar ANOVA model as the model used for the primary endpoint.

Joint Space Width

Minimal JSW (mJSW) in the medial and lateral compartments will be summarised per timepoint (including LOCF) as well as absolute and relative change from baseline for target knee as well as for contralateral knee.

The absolute change from baseline over 2 years will be analysed using an ANOVA model similar to the primary endpoint for target knee only.

Secondary endpoints related to function and symptoms:

WOMAC Total Score

WOMAC total scores (and WOMAC sub scores, as described below) will be displayed descriptively after being transformed to a scale of 0 to 100 using the formula described below.

All items have 11 possible answers ranging from 0 (no problems) to 10 (extreme problems). Given items I1 to Ix as the answers to each questionnaire item on a given subscale and the raw score as the *arithmetic mean* of the respective non-missing answers of items I1 to Ix, the subscale summary score will be calculated as:

$$\left[\frac{(mean\ score\ of\ subscale)}{10}\right]\cdot 100$$

The WOMAC total score, and absolute changes from baseline in the WOMAC total score for the target knee will be presented with summary statistics for all timepoints (including baseline, post-treatment, and LOCF).

Absolute change from baseline in WOMAC total score over 2 years will be considered a continuous variable and will be analysed using a model similar to the ANOVA model used for the primary endpoint.

If an entire questionnaire is missing for a time point, no imputations will be performed for that time point. If some items are missing, imputation for Total score (and for sub scores) will be performed using same principal used for KOOS.

WOMAC Sub Scores

WOMAC sub scores (weight-bearing pain score (sum of items: walking, going up and down stairs, and standing), pain, function and stiffness) will be tabulated descriptively as described above for Total score.

Absolute change from baseline in pain, function, stiffness, and weight-bearing pain, over 2 years will be analysed using a model similar to the ANOVA model described under primary endpoint.

WALK test

Time needed to complete the 20-meter walk tests as well as absolute change from baseline will be presented with summary statistics per timepoint (including LOCF). No imputation for missing data will be done. Absolute change from baseline in time needed to complete the 20-meter walk will be analysed using a model similar to the ANOVA model described under primary endpoint.

Patient Global Assessment (PGA)

The Patient Global Assessment is based on subject's answer to the question "Considering all the ways your osteoarthritis of the knee has affected you during the last 48 Hours, select the number that best describes the impact of your knee osteoarthritis on your daily life", and can take on values between 0-10 (0=None, 10=Extreme), for summaries the values are rescaled to 0-100 by multiplication with 10.

The Patient Global Assessment will be presented with summary statistics per timepoint (including LOCF) as well as absolute change from baseline. Mean score will be presented as described for continuous variables, and also number and percentages per score will be presented. No imputation for missing data will be done (except LOCF).

